7.9.8.2 Adverse Events

All AEs that occur during the study will be recorded and classified on the basis of MedDRA terminology. Treatment-emergent AEs (TEAEs) are defined as AEs with an onset on or after the date of the first study drug application. AEs noted prior to the first study drug administration that worsen after Baseline will also be reported as AEs and included in the summaries.

All information pertaining to an AE noted during the study will be listed by subject, detailing verbatim term given by the investigator or designee, preferred term, system organ class, onset date, resolution date, severity, seriousness, action taken, outcome and drug relatedness. The event onset will also be shown relative (in number of days) to date of first application.

Treatment-emergent AEs will be summarized by treatment group, the number of subjects reporting a TEAE, system organ class, preferred term, severity, relationship to study drug (causality) and seriousness. When summarizing AEs by severity and relationship, each subject will be counted once within a system organ class or a preferred term by using the event with the highest severity and greatest relationship within each classification.

Statistical Analysis Plan for Dermira, Inc. Protocol Number: DRM01B-ACN03

Serious AEs (SAEs) will be summarized by treatment group, severity and relationship to study drug, and individual SAEs will be listed by subject. In addition, a summary of AEs leading to discontinuation from the study due will be provided.

Treatment-emergent AEs will also be summarized by area treated (subjects who treated face only and subjects who treated face plus truncal area or areas).

No statistical inference between treatment groups will be performed on AEs.

Listings will be presented for all AEs as well as for SAEs and AEs leading to discontinuation from the study.

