Pharmacokinetic (PK) results, assessed in a subset of subjects, showed that plasma concentrations of Olumacostat Glasaretil Gel on Day 1 were undetectable for all but 1 subject, who had a plasma concentration of 0.304 at 1 time point (2 hours post-dosing). Plasma concentrations of Olumacostat Glasaretil Gel at Week 8 were undetectable for all tested subjects. Plasma concentrations of TOFA on Day 1 were undetectable in most subjects, but detectable in a few subjects in each dose group, with values ranging from 0.101 to 1.02 ng/mL. Plasma concentration of TOFA at Week 8 were undetectable for most subjects in the DRM01B QD dose groups, but detectable in a few subjects, with values ranging from 0.100 to 0.299 ng/mL. In the Olumacostat Glasaretil Gel, 7.5% BID group, approximately half of the tested subjects had detectable TOFA levels at each time point, with mean values ranging from 0.156 to 0.340 ng/mL.

The most common AEs reported during the study were nasopharyngitis, upper respiratory tract infection, and application site pruritus. Most AEs were mild or moderate in severity. Erythema was the most common LSR. Laboratory values, vital signs, and ECGs measured at the end of the study were generally consistent with baseline values, with no clinically significant trends.

There were no deaths during the study however, one subject in the 7.5% QD group had an SAE of uterine leiomyoma considered unrelated to treatment. Seven subjects prematurely discontinued study drug due to an AE, 4 of these discontinuations were considered to be treatment related.

Study Rationale

Data from the completed Phase 2 dose ranging study, DRM01B-ACN02, and data from study DRM01B-ACN01, have shown that Olumacostat Glasaretil Gel was well tolerated at multiple concentrations. Olumacostat Glasaretil Gel at a strength of 5.0% has been selected as the concentration to take forward in Phase 3 development. Two Phase 3 pivotal trials are planned as part of the Phase 3 development program and will include adults and adolescents (ages 9 years and older) in order to confirm the efficacy and safety of Olumacostat Glasaretil Gel, 5.0% for the treatment of acne vulgaris.

This study, DRM01B-ACN03, is one of the two confirmatory Phase 3 trials being conducted to assess the efficacy and safety of Olumacostat Glasaretil Gel, 5.0% in subjects with acne vulgaris.

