9.4.5 Local Skin Reactions (LSRs)

All subjects will be assessed for LSRs, on the face, at each visit. LSRs include burning/stinging, pruritus, erythema, dryness and peeling. Each LSR will be scored as 0 (None), 1 (Mild), 2 (Moderate) or 3 (Severe). LSRs observed on a visit day will not be recorded as adverse events

unless scored as 3 (Severe). Local skin reactions experienced by the subject in between study visits are to be recorded as an AE.

Burning/stinging and pruritus will be assessed by the subject (Table 3) and erythema, dryness and peeling will be assessed by the Investigator/designee (Table 4). Subjects will be read the definition of each subject-assessed LSR and asked to select the appropriate definition. The corresponding score will be assigned by the site and entered in the eCRF.

Table 3: Subject Assessed Local Skin Reactions

Score	Grade	Burning/Stinging	Pruritus
0	None	No stinging/burning	No pruritus
1	Mild	Slightly warm, tingling sensation; not really bothersome	Occasional, slight itching/scratching
2	Moderate	Definite warm; tingling/stinging sensation that is somewhat bothersome	Intermittent itching/scratching which does not disturb sleep
3	Severe	Hot, tingling/stinging sensation that has caused definite discomfort	Bothersome itching/scratching which disturbs sleep

Table 4: Investigator Assessed Local Skin Reactions

Score	Grade	Erythema	Dryness	Peeling
0	None	None	None	None
1	Mild	Slight erythema: very light- pink	Perceptible dryness with no flakes or fissure formation	Mild diffuse peeling
2	Moderate	Dull red, clearly distinguishable	Easily noted dryness and flakes but no fissure formation	Moderate diffuse peeling
3	Severe	Deep/dark red	Easily noted dryness with flakes and fissure formation	Moderate to prominent, dense peeling

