9.4.8 Dosing Changes due to AEs

Dose interruptions are allowed should a subject experience intolerable treatment-related adverse events (e.g., pruritis) on study. In cases where the Investigator feels a dose interruption is warranted, the subject should be instructed to interrupt study drug application to allow symptoms to resolve. Subjects should be instructed to return to the twice daily application regimen within 2 days of dose interruption.

Dosing interruptions are to be recorded in the subject diary as a missed dose.

Study drug must be discontinued if an adverse event is deemed persistent and if continuation of study drug would not be in the best interest of the subject.

Refer to Section 10.3 for further information regarding discontinuation of study drug or early withdrawal

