11.11 Adverse Events

All AEs that occur during the study will be recorded and classified on the basis of Medical Dictionary for Regulatory Activities (MedDRA) terminology. Treatment-emergent AEs (TEAEs) are defined as AEs with an onset on or after the date of the first study drug application. Adverse events noted prior to the first study drug administration that worsen after baseline will also be reported as AEs and included in the summaries.

All information pertaining to an AE noted during the study will be listed by subject, detailing verbatim term given by the PI or designee, preferred term, system organ class (SOC), onset date, resolution date, severity, seriousness, action taken, outcome and drug relatedness. The event onset will also be shown relative (in number of days) to date of first application.

Treatment-emergent AEs will be summarized by treatment group, the number of subjects reporting a TEAE, SOC, preferred term, severity, relationship to study drug (causality), and seriousness. When summarizing AEs by severity and relationship, each subject will be counted once within a system organ class or a preferred term by using the event with the highest severity and greatest relationship within each classification.

Serious AEs will be summarized by treatment group, severity and relationship to study drug, and individual SAEs will be listed by subject. In addition, a list of subjects who prematurely discontinue from the study due to an AE will be provided.

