7.9 Statistical Analysis

All analyses will be performed by QST. All summary tables and data listings will be prepared utilizing SAS® software. The standard operating procedures of QST will be followed in the creation and quality control of all data displays and analyses.

All data collected at scheduled time points will be summarized, regardless of treatment with study drug. Post-treatment assessments for subjects who discontinue treatment but continued to be followed in the study will be included in summaries.

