7.9.3 Subject Disposition

The number of subjects included in each analysis population (randomized, ITT, safety and PP) will be summarized by treatment group, by treatment group within analysis center and by treatment group within investigational site. The number of subjects completed and discontinued (including the primary reason for discontinuation) will be summarized for each treatment group.

Subjects who are excluded from an analysis population will be summarized by the reasons for exclusion. Reasons subjects were not randomized will be summarized for subjects who did not enroll in the study.

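### AE-discontinuation outputs cover exits from the study only, so a drug stop for an AE with continued follow-up is not tabulated, and a stop for a visit-day skin reaction can score as non-compliance

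*SAP*

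**What the plan says.** The AE outputs are defined by departure from the study. SAP 7.9.8.2 plans "a summary of AEs leading to discontinuation from the study due will be provided" and adds: "Listings will be presented for all AEs as well as for SAEs and AEs leading to discontinuation from the study". Protocol 11.11 is on the same basis: "a list of subjects who prematurely discontinue from the study due to an AE will be provided".

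Elsewhere the documents treat stopping drug and leaving the study as two events. Protocol 10.2 (early termination) and 10.3 (study drug discontinuation) are separate sections. SAP 7.9 states: "Post-treatment assessments for subjects who discontinue treatment but continued to be followed in the study will be included in summaries". The per-protocol (PP) definition in SAP 7.8.4 keeps subjects who stop either treatment or the study for a treatment-related AE, whereas Protocol 11.2 mentions only stopping the study. Disposition in SAP 7.9.3 is a single set of counts: "The number of subjects completed and discontinued (including the primary reason for discontinuation) will be summarized for each treatment group".

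On local skin reactions (LSRs), Protocol 9.4.5 says: "LSRs observed on a visit day will not be recorded as adverse events". The one exception is a score of 3 (severe). The same section makes reactions experienced between visits AEs, with no grade limit. Protocol 9.4.8 says: "Dose interruptions are allowed should a subject experience intolerable treatment-related adverse events (e.g., pruritis) on study". Protocol 9.4.1 asks that new or worsened examination findings after baseline be recorded as AEs.

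**The concern.** A table of AEs leading to discontinuation is where a reader looks to see how many subjects in each arm could not tolerate the gel. Here it answers a narrower question: how many left the study. A subject who stops applying the gel because of an AE and still attends Week 12 has done what SAP 7.9 foresees, but adds nothing to that table. No disposition table reports study-drug completion either.

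The recording rule adds a second route. Pruritus, burning/stinging, erythema, dryness and peeling are the five LSRs. If one is scored 1 or 2 at a visit and drug is stopped or interrupted because of it, Protocol 9.4.5 read literally keeps it out of the AE record. AE status also affects the efficacy populations: SAP 7.9.8.1 excuses missed applications only for treatment-related AEs, and the tolerability-based retention rule in SAP 7.8.4 also requires a related AE. A stop for intolerance could then be scored as failure to comply.

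**Working it through.** The plan states no figure on this point, so there is none to reproduce. The check compares the rules and then does two short calculations.

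**Step 1. Follow three subjects through the planned outputs.**

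| Event | AE-discontinuation summary | Where else it shows |
|---|---|---|
| AE leads to study withdrawal (Protocol 10.2) | Counted | AE tables; disposition with reason |
| AE leads to a drug stop; subject stays to Week 12 (Protocol 10.3, SAP 7.9) | Not counted | AE tables; action taken in the by-subject AE listing; exposure days |
| Grade 1-2 facial LSR, seen only on a visit day, leads to a drug stop | Not counted, not an AE | LSR grade tables; exposure days and missed applications, without reason |

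The second and third rows are the gap. Neither the AE section nor the disposition section gives a by-arm count of them.

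**Step 2. Scale.** Inputs from Protocol 1.2: "Seven subjects prematurely discontinued study drug due to an AE" (4 judged treatment related), and 420 subjects randomized. Planned size is 700 (Protocol 11.14).

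- All AE stops: 7/420 = 1.67%; 0.0167 × 700 = 11.7, about 12.
- Exact binomial 95% interval for 7/420: 0.67% to 3.40%; times 700, 4.7 to 23.8, about 5 to 24.
- Treatment-related stops: 4/420 = 0.95%; times 700, about 7 (exact interval about 2 to 17).

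The assumption is that the Phase 2 rate carries over. The seven are not split by arm in the protocol, and Phase 2 enrolled adults on other strengths and regimens. The documents do not say how many such subjects would remain in follow-up, so the untabulated share runs from none to all. Stops for LSRs never recorded as AEs would be additional and cannot be sized.

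**Step 3. Does an unrecorded LSR stop reach the PP population?** Apply the SAP 7.9.8.1 formulas to a subject who stops at a scheduled visit and attends Week 12, using the target days in SAP 7.9.2 and assuming one application on the first and last dates.

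- Expected applications, Day 1 to Day 85: 2 × (85 − 2) + 1 + 1 = 168.
- Last application at Week 4 (Day 29): total = 2 × (29 − 1 − 1) + 1 + 1 = 56; 56/168 = 33%.
- Last application at Week 8 (Day 57): total = 2 × (57 − 1 − 1) + 1 + 1 = 112; 112/168 = 67%.

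Both fall below the 80% limit, so the subject is non-compliant and leaves the PP population. Had the reaction been recorded as a treatment-related AE, SAP 7.8.4 would retain a subject who discontinued treatment for it. For an interruption, SAP 7.9.8.1 would remove the applications missed between onset and resolution from the expected number.

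A single short interruption does not have this effect. Protocol 9.4.8 has application resume within 2 days; four missed applications give 164/168 = 98%. The compliance consequence therefore concerns stops, not isolated interruptions.

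**The case against.** Four points on the other side carry weight.

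- Protocol 10.2 sends out of the study any subject whose AE, in the investigator's opinion, makes continued treatment or participation contrary to the subject's interest. Many investigator-judged stops therefore already reach the planned table. This stands. What remains is mainly subject-initiated stops, and stops under Protocol 10.3 with continued follow-up.
- Most LSRs bad enough to stop a twice-daily home treatment will also be felt between visits, and Protocol 9.4.5 then makes them AEs at any grade. This too stands. The recording gap is confined to grade 1-2 facial reactions present only as a visit-day observation.
- A reader might infer that Protocol 9.4.8 flatly contradicts 9.4.5. The text does not go that far. Intolerable pruritus can be an AE under both sections if it is grade 3, occurs between visits, or is on the trunk, because LSRs are assessed on the face only. The sections are in tension, as 9.4.1 is with 9.4.5, and should be reconciled.
- Little is lost from the record. A recorded AE stays in the treatment-emergent AE tables, action taken is listed by subject, Protocol 10.1 requires reasons for stopping treatment to be documented, and LSR grades are tabulated by visit and by worst grade. This limits the defect to a missing tabulation. It does not remove it, because a line listing is not a by-arm count.

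**Conclusion.** The point holds as a gap in tabulation with a related recording ambiguity; it is a cheap improvement. The SAP distinguishes stopping drug from leaving the study, but its AE-discontinuation outputs and disposition table do not. On the Phase 2 rate, about 12 of 700 subjects (about 5 to 24) would stop drug for an AE; how many would be left out of the table is unknown. No alpha level, sample size or ITT analysis changes. The PP population can change, through Step 3.

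Three stronger readings are not supported:

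- A reader might infer that drug stops for intolerance will be understated. The documents show only that they can be, for subjects who stop and stay.
- A reader might infer that the Phase 3 count cannot be compared with Phase 2, where the figure is described as stopping study drug. Protocol 1.2 does not say whether those seven also left that study, and no such comparison is planned.
- A reader might treat drug stopping as the main tolerability outcome. SAP 6.2 lists AEs and LSRs among the safety assessments and gives discontinuation no such rank.

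**What to change.** - SAP 7.9.8.2: summarise by arm, and list, AEs leading to discontinuation of study drug and AEs leading to interruption of study drug, beside those leading to study discontinuation. Use the action-taken field that Protocol 9.4.6.1 already collects.
- SAP 7.9.3: report study-drug completion and discontinuation, with reason, separately from study completion and discontinuation.
- Protocol 9.4.5, 9.4.8 and 9.4.1: reconcile the wording so that an LSR leading to interruption or discontinuation of study drug is recorded consistently as an AE. The compliance deduction and PP retention then follow from the existing SAP rules.

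This changes recording and reporting only, and leaves every dosing and stopping rule as it is. The cost is a few sentences and two or three extra tables. Reported AE and discontinuation counts may rise slightly. The changes should be settled before unblinding.

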7.9.8.3 Clinical Laboratory Evaluations

Laboratory test results will be summarized descriptively at Baseline and Week 12. Additionally, shifts from Baseline to Week 12 in laboratory test results based on normal ranges will be summarized with descriptive statistics. Individual laboratory test results will be presented in a by-subject listing.

7.9.8.4 Local Skin Reactions

LSRs include erythema, peeling, dryness, burning/stinging and pruritus. These will be scored as 0 (None), 1 (Mild), 2 (Moderate) or 3 (Severe). LSRs will be summarized by treatment group and visit using descriptive statistics. Each subject's worst post-baseline grade for each LSR will also by summarized. Additionally, the number of subjects who experience mild, moderate or severe LSRs post-baseline will be presented overall, and by visit. By-subject listing of all LSRs, as well as subjects with any severe LSRs will be included.

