8.1 Screening (Day -35 to -1)

The screening evaluation period may take up to 35 days in order to provide adequate washout time for subjects taking certain medications. The purpose of the screening visit is to ensure that appropriate subjects are entered into the study and remain stable during the pre-treatment period. Questions on eligibility will be referred to the Sponsor or their designee. Screen failures may be re-screened one time and must be assigned a new screening number. Screen failure information

will be recorded in the eCRF. Screening procedures, excluding lab evaluations, may be done any time during the screening period (prior to dosing on Day 1) and after the subject has given informed consent.

- Obtain written informed consent/assent. For subjects under legal adult age, both parents or legal representatives may be required to sign informed consent as applicable.
- Collect demographic information
- Complete medical history
- Query subject for concomitant medication use
- Perform a complete physical examination
- Record height and weight
- Measure vital signs
- Assess Inclusion/Exclusion criteria
- Collect a 12 lead ECG
- Draw blood samples for laboratory tests and urine for urinalysis. Include serum pregnancy test for women of childbearing potential
- Determine concomitant medication washout duration
- Schedule next visit

8.2 Baseline Visit/ Day 1

Evaluations are to be done prior to the first dose of study drug

- Collect concomitant medication information
- Conduct a symptom-directed physical exam update medical history if appropriate
- Measure vital signs
- Conduct urine pregnancy test for women of childbearing potential
- Conduct Investigator Global Assessment (IGA)
- Collect acne lesion counts
- Collect Acne Patient Self- Ouestionnaire
- Evaluate face for pre-treatment local skin reactions (LSRs)
- Collect photographs (selected sites)
- Confirm subject eligibility (Inclusion/Exclusion criteria) and randomization to treatment
- Instruct subject on study medication application and diary completion
- Weigh tubes and dispense study drug and diary. Observe subject administering first dose
- Schedule all subsequent visits

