11.12 Local Skin Reactions

Local Skin Reactions (LSRs) include erythema, peeling, dryness, burning/stinging and pruritus. These will be scored as 0 (None), 1 (Mild), 2 (Moderate) or 3 (Severe). LSRs will be summarized by treatment group and visit using descriptive statistics. A by-subject listing of subjects with any LSR 3 or higher will be presented.

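### The post-baseline LSR counts ignore the subject's own Day 1 score, so signs that were present before dosing and persist count as reactions, and no planned summary table shows who worsened

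*SAP*

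**What the plan says.** SAP 7.9.8.4 plans four kinds of LSR display:

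- By visit: "LSRs will be summarized by treatment group and visit using descriptive statistics".
- Worst grade: "Each subject's worst post-baseline grade for each LSR will also by summarized".
- Incidence: "the number of subjects who experience mild, moderate or severe LSRs post-baseline will be presented overall, and by visit".
- By-subject listings of all LSRs and of subjects with severe LSRs.

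Protocol 11.12 plans descriptive statistics by group and visit and a listing of grade 3 scores. Neither section mentions a change from Day 1, a shift table or a rule for worsening.

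The Day 1 score exists. Protocol 8.2 and Appendix 1 have LSRs on the face scored at the Baseline visit before the first dose, and SAP 7.9.1 defines baseline.

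Protocol 9.4.5 governs how LSRs relate to adverse events: "LSRs observed on a visit day will not be recorded as adverse events" unless they score 3 (severe). The same section has reactions that occur between visits recorded as AEs.

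**The concern.** Every subject enters with at least 20 inflammatory facial lesions and an IGA of 3 or more (Protocol 5.3.1). On the scale in Protocol 9.4.5, very light pink skin already scores 1 for erythema. Some subjects may therefore score 1 or more before any study drug is applied. If that score persists, the incidence count treats it as a reaction.

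Other safety data in the SAP are handled differently. For AEs, SAP 7.9.8.2 states: "AEs noted prior to the first study drug administration that worsen after Baseline will also be reported as AEs and included in the summaries". Laboratory tests have shifts from Baseline (7.9.8.3), ECGs have shift tables and treatment-emergent categories (7.9.8.5.1), and vital signs have change from Baseline (7.9.8.5.2). LSRs have no such summary.

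This matters because safety is part of the objective and the product is a topical gel. A rise from 0 to 2 seen at a visit is not an AE under Protocol 9.4.5, so the LSR tables are the main place where it would appear. On the Phase 2 dose-ranging study, Protocol 1.2 reports: "Erythema was the most common LSR". Erythema is also a sign that inflamed skin could show before treatment.

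**Working it through.** The plan gives no LSR rate, so there is no figure to reproduce. The effect of the counting rule can be illustrated.

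**Inputs.** All rates are assumptions.
- b: share of subjects with a Day 1 score of 1 or more, the same in both arms by randomisation; 20%, 40% and 60% are shown.
- p: share of those still scoring 1 or more after baseline; first taken as 1.
- q: new-onset rate among subjects scoring 0 on Day 1; 15% active, 5% vehicle.
- Arm sizes of 467 and 233 come from SAP 4.2.

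**Formulas.** SAP count = b·p + (1−b)·q. New-onset count over all subjects = (1−b)·q.

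**Step 1: equal persistence (p = 1), active vs vehicle.**

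| b | SAP count | Ratio | Difference | New-onset count | Ratio | Difference |
|---|---|---|---|---|---|---|
| 20% | 32% vs 24% | 1.33 | 8 points | 12% vs 4% | 3.0 | 8 points |
| 40% | 49% vs 43% | 1.14 | 6 points | 9% vs 3% | 3.0 | 6 points |
| 60% | 66% vs 62% | 1.06 | 4 points | 6% vs 2% | 3.0 | 4 points |

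For example, at b = 40%: 0.40 + 0.60 × 0.15 = 0.49 and 0.40 + 0.60 × 0.05 = 0.43. The ratio shrinks, but the difference is the same under either count.

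**Step 2: precision of that difference, at b = 40%.**
- SAP count: SE = √(0.49 × 0.51/467 + 0.43 × 0.57/233) = 0.040.
- New-onset count: SE = √(0.09 × 0.91/467 + 0.03 × 0.97/233) = 0.017.

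The same 6 points carry a standard error of about 4.0 points under the SAP count and 1.7 under the new-onset count.

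**Step 3: other assumed rates.** With new onset of 20% active and 10% vehicle and p = 1, a true ratio of 2.0 reads 1.29, 1.13 and 1.06 at b = 20%, 40% and 60%. With p = 0.7 it reads 1.36, 1.18 and 1.09. For p = 1, the chance of a nominal two-sided 5% result would be 56%, 32% and 19% with the SAP count, against 86%, 72% and 52% with the new-onset count. No LSR test is planned, so these percentages only gauge precision.

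**Step 4: unequal resolution.** Take b = 40%, the onset rates of Step 1, and resolution of pre-existing signs by a given visit in 20% on active and 5% on vehicle.
- Active: 0.40 × 0.80 + 0.60 × 0.15 = 0.41.
- Vehicle: 0.40 × 0.95 + 0.60 × 0.05 = 0.41.

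The by-visit count shows no difference, while new onset is 9% vs 3%. These values were chosen to show that cancellation is possible. They do not predict its size.

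**The case against.** A reader might infer that the planned tables hide drug-caused reactions. The documents do not support that as a general statement. Randomisation gives both arms the same expected Day 1 background, and with equal persistence the risk difference matches that of a new-onset count (Step 1). What is lost is relative contrast and precision. Masking needs the unequal resolution of Step 4.

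The plan also gives partial cover:

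- LSRs are scheduled on Day 1, and SAP 7.9 says that data from scheduled time points will be summarised. The by-visit summary should therefore show the Day 1 distribution in each arm.
- A move from mild to moderate or severe can appear in the worst-grade distribution.
- The full listing allows manual comparison.
- Between-visit reactions become AEs, so the LSR tables are not the only view of local tolerability.

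Two further inferences are tempting. One is that the protocol scores LSRs on Day 1 in order to subtract them; it gives no reason. The other is that subjects often arrive with skin irritated by recently stopped topicals. Nothing says how often. Protocol 5.3.2 requires 2 weeks without over-the-counter acne topicals and 4 weeks without prescription topical retinoids on the face, and it excludes skin conditions that may interfere with the safety evaluation.

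All of this limits the size of the problem. The omission stands: the by-visit and worst-grade tables are marginal distributions, and neither they nor the incidence count links a subject's later score to the Day 1 score.

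**Conclusion.** The point holds as a reporting gap. The post-baseline count and the worst-grade summary ignore a Day 1 score that is collected, so persistent pre-existing signs are reported as reactions and no planned summary table shows who worsened.

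Under the Step 1 assumptions, a ratio of 3.0 reads between 1.33 and 1.06, with the absolute difference unchanged and less precisely estimated. That size rests on assumed Day 1 prevalence, onset and full persistence. The documents supply none of these, and at a prevalence near zero the problem disappears.

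LSRs are descriptive safety data and no efficacy conclusion depends on them. The change is worth making because it is cheap and makes the tolerability comparison more informative.

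**What to change.** In SAP 7.9.8.4, for each LSR and treatment arm, add:

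1. a shift table of Day 1 score by worst post-baseline score;
2. the number and percentage of subjects whose post-baseline score exceeds their Day 1 score, overall and by visit.

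Present these alongside the planned tables. Stating explicitly that the by-visit summary includes Day 1 would remove any doubt on that point.

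The cost is SAP wording and extra table shells. The data are already collected, the additions fit the descriptive approach of Protocol 11.12, and they can be specified before unblinding. The downside is that the worsening count misses a reaction that clears and then returns only to the Day 1 grade. For that reason the planned tables should be kept rather than replaced.
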